5.3.4 Investigational Medicinal Product Accountability

The investigator has overall responsibility for the accountability of all used and unused IMP. A drug accountability record for the IMPs must be kept current and should contain:

- The dates and quantities of IMP received from GWP.

- Patient's identification.
- Date and quantity of IMP dispensed.
- The initials of the dispenser.
- Date and quantity of IMP returned to the investigator/pharmacy.

A record of returned IMP must be completed and included in the shipment of used and unused IMP to GWP. At the end of the study a record/statement of reconciliation must be completed and provided to GWP.

These inventories must be made available for inspection by authorized GW or GWP representatives and local officials or regulatory agency inspectors.

Please refer to the separate Pharmacy Manual for more detailed information on the IMP.

5.4 Clobazam

Patients will use their own supply of CLB throughout the study. CLB usage will be recorded by the investigator. CLB is only an IMP for the blinded phase of the study.

6. PARTICIPANT ELIGIBILITY

Investigators will be required to maintain a log that includes limited information about all screened patients (initials, age, and gender; as allowed per local regulations) and outcome of screening.

6.1 Inclusion Criteria

For inclusion in the study patients must fulfil ALL of the following criteria:

- 6.1.1 Male or female patients aged 18 to 65 years inclusive.
- 6.1.2 Patient must have epilepsy as determined by the investigator and be taking CLB.
- 6.1.3 Patient must have a documented magnetic resonance imaging/computerized tomography of the brain that ruled out a progressive neurologic condition.
- 6.1.4 Patient must have experienced at least one seizure of any type (i.e., convulsive: tonic-clonic, tonic, clonic, atonic; focal: focal seizures with retained consciousness and a motor component, focal seizures with impaired consciousness focal seizures evolving to bilateral secondary generalization) within the two months prior to randomization.
- 6.1.5 Patients must be taking CLB and no more than two other AEDs during the course of the study.
- 6.1.6 AED(s), including CLB, must be stable for four weeks prior to screening and regimen must remain stable throughout the duration of the blinded phase of the study.

- 6.1.7 Intervention with vagus nerve stimulation (VNS) and/or ketogenic diet must be stable for four weeks prior to baseline and patient/caregiver must be willing to maintain a stable regimen throughout the blinded phase of the study.
- 6.1.8 Patients must abstain from alcohol during the blinded phase of the study.
- 6.1.9 Patient is available to attend all PK visits within the required visit window.
- 6.1.10 Patient and/or legal representative must be willing and able to give informed consent for participation in the study
- 6.1.11 Patient and/or legal representative must be willing and able (in the investigator's opinion) to comply with all study requirements.
- 6.1.12 Patient is willing for his or her name to be notified to the responsible authorities for participation in this study, as applicable.
- 6.1.13 Patient is willing to allow his or her primary care practitioner and consultant, if appropriate, to be notified of participation in the study.

6.2 Exclusion Criteria

The patient may not enter the study if ANY of the following apply:

- 6.2.1 Patient has clinically significant unstable medical conditions other than epilepsy.
- 6.2.2 Patients on CLB at doses above 20 mg per day.
- 6.2.3 Patients taking CLB intermittently as rescue medication.
- 6.2.4 Patient has a history of symptoms (e.g., dizziness, light-headedness, blurred vision, palpitations, weakness, syncope) related to a drop in blood pressure (BP) due to postural changes.
- 6.2.5 Any history of suicidal behavior or any suicidal ideation of type four or five on the C-SSRS in the last month or at screening.
- 6.2.6 Patient has had clinically relevant symptoms or a clinically significant illness in the four weeks prior to screening or enrollment, other than epilepsy.
- 6.2.7 Patient has consumed alcohol during the seven days prior to enrollment and is unwilling to abstain during the blinded phase of the study.
- 6.2.8 Patient is currently using or has in the past used recreational or medicinal cannabis, or synthetic cannabinoid based medications (including Sativex[®]) within the three months prior to study entry.
- 6.2.9 Patient has any known or suspected history of any drug abuse or addiction.
- 6.2.10 Patient is unwilling to abstain from recreational or medicinal cannabis, or synthetic cannabinoid based medications (including Sativex) for the duration of the study.
- 6.2.11 Patient has consumed grapefruit or grapefruit juice seven days prior to enrollment and is unwilling to abstain from drinking grapefruit juice within seven days of PK visits.
- 6.2.12 Patient has any known or suspected hypersensitivity to cannabinoids or any of the excipients of the IMP, e.g., sesame oil.

6.2.13 Female patient is of child bearing potential, or male patient's partner is of child bearing potential; unless willing to ensure that they or their partner use highly effective contraception for the duration of the study and for three months thereafter. Highly effective methods of contraception are defined as those, alone or in combination, that result in a low failure rate (i.e., less than 1% per year) when used consistently and correctly. Such methods include hormonal contraceptives, intrauterine devices/hormone-releasing systems, bilateral tubal occlusion, vasectomized partner or sexual abstinence.

6.2.14 Female patient who is pregnant (positive pregnancy test), lactating or planning pregnancy during the course of the study and for three months thereafter.

6.2.15 Patients who have received an IMP within the 12 weeks prior to the screening visit.

6.2.16 Patient is taking felbamate and they have been taking it for less than one year prior to screening.

6.2.17 Any other significant disease or disorder which, in the opinion of the investigator, may either put the patient at risk because of participation in the study, may influence the result of the study, or the patient's ability to participate in the study.

6.2.18 Following a physical examination, the patient has any abnormalities that, in the opinion of the investigator would prevent the patient from safe participation in the study.

6.2.19 Patient has significantly impaired hepatic function at screening (Visit 1) or enrollment (Visit 2), defined as any of the following:

- Alanine aminotransferase (ALT) or Aspartate aminotransferase (AST) $> 5 \times$ upper limit of normal (ULN).
- ALT or AST $> 3 \times$ ULN **and** total bilirubin (TBL) $> 2 \times$ ULN **or** international normalized ratio (INR) > 1.5 .
- ALT or AST $> 3 \times$ ULN with the presence of fatigue, nausea, vomiting, right upper quadrant pain or tenderness, fever, rash, and/or eosinophilia ($> 5\%$).

*This criterion can only be confirmed once the laboratory results are available; patients randomized into the study who are later found to meet this criterion **must** be withdrawn from the study.*

6.2.20 Patient has a prolonged QTcB (> 450 msec for males and > 470 msec for females).

6.2.21 Unwilling to abstain from donation of blood during the study.

6.2.22 Travel outside the country of residence planned during the study, unless the patient has confirmation that the IMP is permitted in the destination country/state.

6.2.23 Patients previously enrolled into this study.

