C _{max}	Maximum measured plasma concentration
CRF	Case Report Form
CRO	Contract Research Organization
C-SSRS	Columbia-Suicide Severity Rating Scale
CYP	Cytochrome P450
EC	Ethics Committee
ECG	12-lead electrocardiogram
EU	European Union
GCP	Good Clinical Practice
GW	GW Research Ltd
GWP	GW Pharma Ltd
IB	Investigator Brochure
ICH GCP	International Conference on Harmonization Tripartite Guideline for Good Clinical Practice
IMP	Investigational Medicinal Product
IND	Investigational New Drug
INR	International Normalized Ratio
IRB	Institutional Review Board
ITT	Intention to Treat

IVRS	Interactive Voice Response System
LEV	Levetiracetam
LOCF	Last Observation Carried Forward
MMRM	Mixed-effects Model Repeated Measures
N-CLB	N-desmethylclobazam
OLE	Open label extension
PBPK	Physiologically-based pharmacokinetic interactions
PI	Principal Investigator
PP	Per Protocol
PVD	Pharmacovigilance Department
QTcB	Heart rate corrected QT interval using Bazett's formula
SAE	Serious Adverse Event
SAP	Statistical Analysis Plan
SFU	Safety follow up
STP	Stiripentol
SUSAR	Suspected Unexpected Serious Adverse Reaction
$t_{1/2}$	Terminal half-life
TBL	Total bilirubin
THC	Δ^9 -tetrahydrocannabinol
t_{max}	Time to the maximum measured plasma concentration
TPM	Topiramate
ULN	Upper Limit of Normal
USA	United States of America
VNS	Vagus Nerve Stimulation
VPA	Valproate

Definition of Terms

Term	Definition
Baseline period	The period from screening (Visit 1) to enrollment (Visit 2).
Convulsive seizures	Tonic-clonic, tonic, clonic or atonic seizures.
Countable partial seizures	Partial/focal seizures with a motor or behavioral component that allow such seizures to be easily identified and hence counted.
Day 1	The day a patient is enrolled and begins PK sampling.
End of treatment	Completion of the treatment period (Visit 5 or Visit 12) or withdrawal.
End of study	Last patient's last visit / last contact.
IMP	Investigational Medicinal Product (Study Medication). Used to describe both investigational active product and reference therapy (placebo).
INR	International Normalized Ratio (INR) is a calculation made to standardize prothrombin time.
Investigator	Study Principal Investigator or a formally delegated study physician.
Non-convulsive seizures	Myoclonic, partial or absence seizures.
Partial seizures	Partial (focal) seizures occur when the electrical activity remains in a limited area of the brain.
Status epilepticus	Seizures lasting for 30 minutes or longer.

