4. EXPERIMENTAL PLAN

4.1 Study Design

This phase 2, placebo-controlled study consists of a 34 day, double-blind phase followed by an optional maximum one year OLE. Patients will continue to take CLB as advised by their physician for the duration of the study. GWP42003-P/placebo will be taken twice daily immediately after their CLB dose.

Patients will enter the study and begin a 10 day GWP42003-P or placebo titration phase. During this period patients will be up-titrated to a maintenance dose or equivalent of 20 mg/kg/day. Patients will continue to take this maintenance dose of GWP42003-P or placebo for 21 days (Days 12 to 32).

Upon completion of the treatment period (Day 34) patients will be invited to receive GWP42003-P during the OLE phase. If a patient enters the OLE they will take GWP42003-P as advised by the investigator. If a patient chooses not to enter the OLE, and/or the investigator does not feel it is in their best interests, they will taper off their GWP42003-P/placebo treatment by reducing their maintenance dose by 10% per day until dosing has ceased. For those patients not entering the OLE, dosing will end on Day 43 and they will receive a telephone follow-up visit four weeks after the end of GWP42003-P/placebo dosing (Day 71).

PK samples will be taken on two occasions during the blinded phase of the study:

- Day 1 (Visit 2) before beginning treatment (patients will be taking CLB only).
- Day 33 (Visit 4) following 21 days of GWP42003-P or placebo maintenance (patients will be taking CLB and GWP42003-P or placebo).

Ten samples will be taken during each PK assessment. PK samples should be taken at time points in respect to the morning dose of CLB. The time points are as follows: Pre-dose, 15 min, 30 min, 1 h, 1.5 h, 2 h, 4 h, 6 h, 12 h and 24 h. PK samples will be quantitatively analyzed for CLB, N-CLB, valproate (VPA), stiripentol (STP), levetiracetam (LEV) and topiramate (TPM) at Visit 2 and CLB, N-CLB, VPA, STP, LEV, TPM, CBD, CBD major metabolites, THC and THC major metabolites at Visit 4.

Patients should try to be consistent in the timing of their food intake in relation to dosing throughout the blinded phase of the study.

Upon entry into the OLE the dose of GWP42003-P and other AEDs may be adjusted up or down to a maximum of 30 mg/kg/day. The OLE will last for a maximum of one year or until marketing authorization is granted; whichever is earlier.

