7. PATIENT ENROLLMENT

Before patients may be entered into the study, GW requires a copy of the relevant center's Ethics Committee (EC) or Institutional Review Board (IRB) written approval of the protocol, informed consent forms (ICFs) and other patient information material. Patients will be considered enrolled in the study from the time of providing written informed consent. All patients, or legal representatives, where appropriate, must personally sign and date the consent form prior to any procedures being performed (refer to [Section 9.1.2](#) and [Section 15.2](#)).

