9.1.9 Clinical Laboratory Sampling

Laboratory tests will be undertaken at all hospital visits and will include hematology, biochemistry, and urinalysis (provided urine can be obtained, with the exception of

screening where a urine sample for THC screen must be obtained). A serum alcohol test will be performed at Visits 1, 2 and 4. A serum pregnancy test (if appropriate) will also be performed at Visit 1.

Urine samples for biochemistry will be analyzed at the study center by use of a dipstick with any relevant findings being sent for further laboratory based urinalysis (urinalysis, microscopy, culture and sensitivity, as applicable).

The investigator and study monitor will be provided with a list of the normal ranges used by the testing laboratory for all variables assayed during the study and a statement of accreditation (or similar) for the laboratory. Clinical laboratory sample parameters are detailed in [Table 9.1.9-1](#).

Table 9.1.9-1 Hematology, Biochemistry, Urinalysis and THC Screen

Biochemistry (serum)	Hematology (whole blood)	Urinalysis (urine)	Pregnancy Test	THC screen (urine)
Alanine aminotransferase (ALT)	Hematocrit	Bilirubin	Serum	THC
Albumin	Hemoglobin	Blood		
Alkaline phosphatase	Mean cell volume	Glucose		
Aspartate aminotransferase (AST)	Mean corpuscular hemoglobin	Ketones		
Calcium	Platelets	Nitrites		
Creatinine	Red blood cell count	pH		
Estimates of glomerular filtration rate	White blood cell count with automated differential	Protein		
Gamma-glutamyl transferase		Specific gravity		
Glucose		Urobilinogen		
HDL-cholesterol				
Potassium				
Prolactin				
Prothrombin time (plasma)				
Sodium				
Total bilirubin (TBL)				
Total protein				
Urea (BUN)				
Triglycerides				

All laboratory results will be reviewed and the reports signed by an investigator. Any results considered to be of clinical significance must be addressed and followed up as clinically appropriate. See [Section 12.8](#) for guidance on evaluation of potential drug-induced liver injury. All laboratory results considered by the investigator to represent an AE must be documented on the CRF.

Repeat samples will be taken, if required, for clinical follow up or if the sample is lost or damaged. Any abnormal end of treatment clinical laboratory result of clinical significance must be repeated at regular intervals until it returns to normal, or until an

investigator is satisfied that the abnormality is not related to the IMP and needs no further investigation.

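### Exclusion 6.2.11 joins recent grapefruit intake and unwillingness to abstain with *and*, so either one alone leaves a patient eligible and a PK profile may be affected

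*Protocol*

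**What the plan says.** The list in Protocol Section 6.2 opens with "The patient may not enter the study if ANY of the following apply". One criterion is enough to exclude, but each criterion has to be met in full.

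Item 6.2.11 reads "Patient has consumed grapefruit or grapefruit juice seven days prior to enrollment and is unwilling to abstain from drinking grapefruit juice within seven days", and the sentence ends by tying those last seven days to the PK visits. The synopsis carries the same wording. Item 6.2.7 has the same structure for alcohol: "Patient has consumed alcohol during the seven days prior to enrollment and is unwilling to abstain during the blinded phase of the study". For alcohol there is also inclusion criterion 6.1.8, "Patients must abstain from alcohol during the blinded phase of the study", and Section 9.1.9 states "A serum alcohol test will be performed at Visits 1, 2 and 4", without saying what follows from a positive result.

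Section 4.1 places the reference PK profile at "Day 1 (Visit 2) before beginning treatment (patients will be taking CLB only"; the second profile is at Visit 4 (Day 33).

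The look-back runs back from enrollment, which the protocol defines in two ways. Section 7 has "Patients will be considered enrolled in the study from the time of providing written informed consent"; the Definition of Terms describes Day 1 as "The day a patient is enrolled and begins PK sampling".

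**The concern.** The purpose of a grapefruit rule in a clobazam interaction study is presumably to keep a possible influence on metabolism out of both PK profiles. That needs two separate conditions: no recent intake before the first profile, and agreement to abstain before both. Joined by *and*, neither condition excludes anyone by itself.

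The primary objective is whether GWP42003-P changes the PK of clobazam and N-desmethylclobazam, and the model in Section 13.6.3 compares clobazam plus CBD with clobazam alone, with subject as a random effect. An influence present at one visit only goes straight into that patient's ratio. If it raises exposure at Visit 2, the ratio is pulled down; if it does so at Visit 4, the ratio is pushed up. With 20 patients and an analysis that Section 13.1 calls descriptive, the estimated ratio is the main product of the study.

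**Working it through.** **1. Logic of 6.2.11.** The four possible patients:

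| Intake in the look-back week | Abstain from juice around PK visits | As written (*and*) | With *or* |
|---|---|---|---|
| No | Willing | Eligible | Eligible |
| No | Unwilling | Eligible | Excluded |
| Yes | Willing | Eligible | Excluded |
| Yes | Unwilling | Excluded | Excluded |

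The present wording excludes one of the four. The two middle rows are the gap.

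**2. Does anything else close it?** For grapefruit, no explicit rule does.

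- Section 8.3 (prohibited therapy) does not list it.
- The Visit 2 and Visit 4 procedures in Section 9.2.1 contain no grapefruit check.
- The diary in Section 9.1.13 covers seizures, adverse events, antiepileptic and rescue medication, and study drug intake.
- The dietary instruction in Section 4.1 concerns consistent timing of food only.

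**3. Comparison within the protocol.** For cannabis, past use (6.2.8) and unwillingness to abstain (6.2.10) are two separate criteria, and either one excludes. The same two ideas are fused in 6.2.7 and 6.2.11.

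**4. Fruit and juice.** The intake part of 6.2.11 names grapefruit and its juice. The abstinence part names juice only.

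**5. Anchor of the look-back.** Visit 2 takes place 7–14 days after Visit 1. If enrollment means consent at Visit 1, the look-back covers 7 + 7 = 14 down to 7 days before Visit 2 at the shortest interval, and 14 + 7 = 21 down to 14 days at the longest. In neither case does it cover the week immediately before the reference profile. If enrollment means Day 1, it does.

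**6. Possible size.** The protocol states no figure for a grapefruit effect, so there is nothing to reproduce and the following is an illustration.

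- Active patients: 20 × 4/5 = 16 (Section 7.2, 4:1 allocation).
- Assumed: grapefruit multiplies clobazam exposure by k = 1.2 to 1.5.
- Assumed: m = 1 or 4 active patients are affected, at Visit 2 only.
- Assumed: the ratio rests on complete pairs from the 16 active patients, so the log ratio is the mean of the within-patient log differences.

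Each affected patient's log ratio falls by ln k, so the geometric mean ratio is multiplied by k^(−m/16).

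| | k = 1.2 | k = 1.5 |
|---|---|---|
| m = 1 | 1.2^(−1/16) = 0.989 | 1.5^(−1/16) = 0.975 |
| m = 4 | 1.2^(−4/16) = 0.955 | 1.5^(−4/16) = 0.904 |

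If the same patients were affected at Visit 4 only, the factor would be the inverse, from 1/0.989 = 1.01 to 1/0.904 = 1.11.

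**7. Against the no-effect boundary.** At the extreme of 0.904, and ignoring any change in interval width, only an upper confidence limit that should lie between 2.00 and 2.0/0.904 = 2.21 would be drawn inside [0.5, 2.0].

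**The case against.** The best defence is that the abstinence part of 6.2.11 speaks of PK visits in the plural, and Visit 2 is one of them. Screening is at least seven days earlier, so a patient who declares willingness at Visit 1 has agreed to avoid juice before the reference profile too, and eligibility is checked again on Day 1. This stands and narrows the gap. What stays open is actual intake despite stated willingness, the fruit as distinct from the juice, and the non-consumer who is unwilling.

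A second argument is that 6.1.11 requires willingness to comply with all study requirements, which might catch the unwilling non-consumer. It might, but no section outside 6.2.11 states grapefruit abstinence as a requirement, so this depends on the reader. The absence of grapefruit from Section 8.3 proves little by itself, because that list concerns medications and interventions.

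Third, the alcohol criterion is much less exposed. Item 6.1.8 already demands abstinence in the blinded phase, and Section 4.1 places both PK occasions inside that phase. Only the week before Day 1 is open, given that Section 4.1 counts the double-blind phase as 34 days; even that would close if the phase included screening, as the heading of Section 9.2.1 suggests. The documents describe no effect of alcohol on clobazam PK. A reader might infer that alcohol threatens the primary ratio as grapefruit does; the text does not support that.

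Finally, the illustrated bias is small beside a boundary of [0.5, 2.0]. That is fair.

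**Conclusion.** The wording defect is certain: 6.2.11 excludes only patients who meet both halves, and this defeats its apparent purpose. That the reference or the Visit 4 profile may be affected is a possibility, not an established fact. A reader might infer that the clobazam-only profile is contaminated, or that every recent consumer gets in. Neither follows: no section quantifies a grapefruit effect on clobazam or its metabolite, and a recent consumer who is also unwilling to abstain remains excluded.

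Under the assumed 20–50% effect in 1 to 4 of 16 active patients at Visit 2 only, the ratio is multiplied by about 0.99 to 0.90. The lower end needs a quarter of the active arm affected and the top of the assumed range. This would shade the estimate rather than overturn the conclusion, but the correction costs so little that it should be made.

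**What to change.** - Split 6.2.11 into two criteria, one for intake and one for unwillingness to abstain, following 6.2.8 and 6.2.10; replacing *and* with *or* has the same effect. Change the synopsis to match.
- Name both the fruit and the juice in each part.
- Anchor the seven-day look-back to Visit 2 Day 1 instead of to enrollment, and reconcile the two definitions of enrollment.
- Make the same conjunction change in 6.2.7 for consistency, recognising that 6.1.8 already covers alcohol in the blinded phase and that only the week before Day 1 is affected.

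The cost is a short wording amendment. Patients told at Visit 1 can complete seven clean days within the existing 7–14 day interval, so at worst an occasional Visit 2 falls later in that interval or its 3-day window. A patient with intake close to Visit 2 could need up to seven more days; where that runs past the window, the patient would not be enrolled. An entry criterion cannot control actual intake before Visit 4; there the change secures only the patient's agreement.
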